4.2 Inclusion criteria

1. Male and female subjects aged 18 to 65 years*
2. Body Mass Index (BMI) between 18 and 30 kg/m² (self-reported)
3. Ulcerative Colitis confirmed via previous endoscopy and histology
4. Mild active UC as defined by P-SCCAI score of 3 to 5 (range 0 to 19)
5. Frequent relapse (at least one exacerbation in the last two years)
6. No known allergy to any components of the study product (self-reported)
7. Signed informed consent
8. Stable UC medication defined as no switch to other medication or no dose change
9. Mobile phone on which apps (used for questionnaires) can be downloaded (iOS version 9 and newer, Android version 4.4 and newer. Phones manufactured after 2013 are usually suitable)
10. Stable dietary pattern during the study

* We only include adults (age 18-65) as previous studies have shown that adolescent and elderly microbiota as well as UC presentation in adolescents can be different from adults[32, 33].

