5. TREATMENT OF SUBJECTS

5.1 Investigational product/treatment

In this study, all 60 participants will undertake an 8-week intervention with either a prebiotics supplement (arm 1 and 3) or a placebo supplement (arm 2 and 4), which will be consumed once per day (1 sachet in the morning) during the first week, and twice per day (1 sachet in the morning and 1 sachet in the evening) for the remainder of the intervention. During the entire trial, research subjects will maintain their normal routines concerning their diet, medication use, and exercise pattern.

Prebiotics supplement: Prebiotics preparation is composed of three individual fibers (40% acacia gum, 20% partially hydrolyzed guar gum, and 40% resistant starch) from Winclove Probiotics B.V. (Amsterdam, the Netherlands).

Placebo (control): Placebo preparation is composed of food-grade corn starch and maltodextrin from Winclove Probiotics B.V. (Amsterdam, the Netherlands).

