8.1.2 Secondary study parameters/endpoints

Response over time

In addition to week 8, subjects need to fill out the P-SCCAI questionnaire at T = 0, 4, 12, and 60 weeks to determine the response over time. Comparisons will be made between groups as well as within subjects over time. With P-SCCAI score <= 2 being regarded as clinical remission, and a decrease in the P-SCCAI score by more than two points from baseline being regarded as clinical response [30, 31, 55] (see F1). We will also determine whether subjects have reached clinical remission and/or showed a clinical response over time.

Mucosal inflammation

At T= 0, 8, 12, and 60 weeks, a fecal sample will be provided by subjects for calprotectin measurement.

GI complaints: (e.g. abdominal pain, bloating, flatulence)

At T= 0, 4, and 8 weeks, the GI complaints will be assessed by the GSRS questionnaire. The GSRS contains 15 items clustered into five domains (reflux, abdominal pain, indigestion, diarrhea and constipation) addressing different gastrointestinal symptoms [56]. It has a seven-point graded scale where 1 represents the absence of troublesome symptoms and 7 represents very

troublesome symptoms (see F1). The reliability and validity of the GSRS are well-documented, and norm values for a general population are available [57].

Stool consistency and frequency

At T = 0, 4, and 8 weeks, subjects will be asked to keep diaries to record stool frequency (bowel movement per day) and consistency of each stool using Bristol stool form scale (see F1) on a daily basis for 7 days.

Gut microbiota and SCFAs: (e.g. microbiota composition, SCFAs profile)

At T = 0, 8, 12, and 60 weeks, a fecal sample will be provided by subjects for 16S rRNA gene-based microbiota profiling and SCFAs measurement. Subsequent analyses of a variety of microbial ecological characteristics, including microbiota composition, α -diversity (diversity within the sample), β -diversity (diversity between the samples), population dynamics over time, and group differences will also be conducted.

Health-related quality of life

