At T = 0, 4, and 8 weeks, health-related quality of life will be assessed by the SIBDQ questionnaire (see F1). SIBDQ is a 10 item shortened version of the original IBDQ which was 32 items. It has a seven-point graded scale where 1 represents very troublesome symptoms and 7 represents the absence of troublesome symptoms. Measures quality of life as measured in four domains (bowel symptoms, emotional health, systemic systems and social function) [58]. Its reliability and responsiveness to change has been validated in UC [59].

Medication use

At T= 0, 4, 8, 12 and 60 weeks, information of medication use will be extracted from patient record and diary. It consists of the current medication use (e.g., aminosalicylates, corticosteroids, immunosuppressive agents, antimicrobial agents, and inhibitors of tumour necrosis factor-alpha (TNF- α)). Medication changes at week 4, 8, 12, and 60 provide information on disease development, with a downgrade means improvement and an upgrade means worsening of UC.

Safety parameters

At T= 0, 4, and 8 weeks, safety parameters (i.e., incidence of adverse events) will be monitored by patient record and diary. In this diary, all relapse-relevant information, including the need for systemic steroids, hospitalization, and surgery will be collected.

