10.2 Secondary study parameter(s)

Response over time

To assess the response over time, data of mean P-SCCAI score within each arm at T = 0, 4, 8, 12 and 60 weeks will be obtained. Comparisons will be made between groups (as done for T = 8 for the primary study parameter) as well as within subjects over time. With P-SCCAI score ≤ 2 being regarded as clinical remission, and a decrease in the P-SCCAI score by more than two points from baseline being regarded as clinical response, we will determine whether subjects have reached clinical remission and/or showed a clinical response over time.

To assess the response within each subject (clinical remission and/or clinical response) over time, data of sum P-SCCAI score within each subject at T = 0, 4, 8, 12 and 60 weeks will be obtained. For comparative analyses between baseline and intervention, the parametric paired sample T-test or the non-parametrical Kruskal-Wallis or Mann-Whitney

U test will be used, depending on the distribution of the samples. Differences between treatments before and after supplement intake will also be analysed by linear mixed models for repeated measures, using “treatment” [prebiotics/placebo], “responding” [responders/non-responders], “time point” [0, 4, 8, 12 and 60 weeks] and “treatment x responding x time point” as fixed effects and subject as random effect. Clinically relevant variables such as BMI, age, sex, and medication use will be taken into account.

Mucosal inflammation

Fecal calprotectin data will be analysed in the same manner as described above (Response over time).

GI complaints:

Data from GSRS will be computed into scores, and the score of each item will be pooled together as the sum score, and the score of each item within each domain will be pooled as well. All data will be analysed in the same manner as described above (Response over time). Differences over time within and between groups will be tested with mixed model analysis. Variables such as timepoint, group, age, sex will be taken into account.

Stool consistency and frequency

Average bowel movement per day and dynamic change on stool consistency will be calculated and collected. All data will be analysed in the same manner as described above (Response over time)..

Gut microbiota and SCFAs

Fecal SCFAs data will be analysed in the same manner as described above (Response over time)

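### Remission and response rest on the P-SCCAI score alone to week 60, so retained subjects with a UC medication upgrade can count as successes while those withdrawn for an exacerbation become missing

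*Protocol*

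**What the plan says.** All references are to the protocol.

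- **Definitions.** Section 8.1.2 (Response over time) sets remission with "With P-SCCAI score <= 2 being regarded as clinical remission" and response with "a decrease in the P-SCCAI score by more than two points from baseline being regarded as clinical response". Neither carries a condition on medication.
- **Analysis.** Section 10.2 repeats both definitions and says "we will determine whether subjects have reached clinical remission and/or showed a clinical response over time". For this, "data of sum P-SCCAI score within each subject at T = 0, 4, 8, 12 and 60 weeks will be obtained".
- **Medication use.** Section 8.1.2 interprets changes at weeks 4, 8, 12 and 60, "with a downgrade means improvement and an upgrade means worsening of UC". The safety paragraph adds that "all relapse-relevant information, including the need for systemic steroids, hospitalization, and surgery will be collected". Neither statement is linked to remission or response.
- **Medication stability.** Section 4.2 requires "Stable UC medication defined as no switch to other medication or no dose change", and section 5.1 expects that "research subjects will maintain their normal routines concerning their diet, medication use, and exercise pattern". Neither says how to classify a subject whose medication does change.
- **Withdrawal.** Section 8.4 leaves withdrawal for newly started interfering medication to the investigator's decision. Section 8.4.1 makes withdrawal the rule for serious GI complaints or a reported UC exacerbation. Section 8.6 provides no follow-up after withdrawal, apart from an exception for other medical reasons.

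**The concern.** At one visit, the same subject can be worse on the medication endpoint and in remission on the score endpoint. That matters because added UC therapy lowers symptom scores. A remission reached after an upgrade cannot be credited to the supplement with any confidence, least of all at weeks 12 and 60, when supplementation has ended.

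The threshold is also easy to reach. Subjects enter with a score of 3 to 5, so someone who enters at 3 is in remission after a one-point fall.

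Subjects who do badly can take one of two routes. Those upgraded and retained can become successes. Those withdrawn for an exacerbation generally drop out of the data. Neither route records them as a failure on remission or response, and which route applies depends partly on investigator discretion. If the routes are used unequally across arms, the secondary comparisons are distorted.

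**Working it through.** **1. Does the plan have a figure that depends on this?** No. Its only size calculation (section 4.4) concerns mean P-SCCAI at week 8. With means 3.5 and 2.8, SD 0.5, two-sided α 0.05 and power 0.90, the normal approximation gives n = 2 × (1.960 + 1.282)² / (0.7/0.5)² = 21.0 / 1.96 = 10.7. That rounds to 11 per group, as stated. No remission, response or upgrade rate enters, so nothing there changes.

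**2. How the rules classify a subject after an upgrade or exacerbation.**

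| Subject | Rule that applies | Status on remission or response |
|---|---|---|
| Upgraded, retained, score criterion met | 8.1.2 and 10.2; 8.4 not used | Success |
| Upgraded, retained, score criterion not met | 8.1.2 and 10.2 | Not a success |
| Withdrawn for interfering medication | 8.4, then 8.6 | Generally no later score: missing |
| Withdrawn for UC exacerbation | 8.4.1, then 8.6 | Generally no later score: missing |

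The first row can occur. Withdrawal under 8.4 is discretionary. Subjects enter with active disease and could be stepped up for persisting symptoms without an exacerbation. Section 8.1.2 also reads medication changes as an outcome up to week 60.

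**3. Effect of the first row (illustration; every rate is assumed).** For each arm let r be remission without upgrade, u the share upgraded and retained among all subjects (drawn from those otherwise not in remission), and q the share of these who then score 2 or less. The score-only rate is r + u × q. With the same q in both arms, the difference shifts by (u₁ − u₂) × q, where arm 1 is the better arm.

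| r (arm 1 v 2) | u (arm 1 v 2) | q | Score-only rates | Difference, score-only | Difference, upgrade = failure |
|---|---|---|---|---|---|
| 50% v 20% | 5% v 15% | 50% | 52.5% v 27.5% | 25 points | 30 points |
| 50% v 20% | 5% v 15% | 80% | 54% v 32% | 22 points | 30 points |
| 50% v 20% | 10% v 30% | 50% | 55% v 35% | 20 points | 30 points |
| 50% v 20% | 10% v 30% | 80% | 58% v 44% | 14 points | 30 points |
| 40% v 20% | 10% v 30% | 80% | 48% v 44% | 4 points | 20 points |
| 50% v 20% | 30% v 10% | 50% | 65% v 25% | 40 points | 30 points |
| 50% v 20% | 30% v 10% | 80% | 74% v 28% | 46 points | 30 points |

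Worked example, fourth row: 0.50 + 0.10 × 0.80 = 0.58 and 0.20 + 0.30 × 0.80 = 0.44. The shift is (0.10 − 0.30) × 0.80 = −16 points, and 30 − 16 = 14. Equal upgrade shares give no shift.

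**4. Effect of the withdrawal rows (illustration).** Take an arm of 15 with 3 remitters and 3 subjects withdrawn for an exacerbation. If only those with a score are counted (an assumption), remission is 3/12 = 25%. If the withdrawn count as failures, it is 3/15 = 20%. One subject in 15 is 6.7 points, so a few subjects matter.

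**The case against.** **Endpoint choice.** Scoring symptoms whatever therapy has been added, and reporting medication change as its own endpoint, is a legitimate design. Two endpoints that disagree at one visit are not in themselves a contradiction. That is fair. But the protocol does not say it has chosen this, and its withdrawal rules do not allow it to be carried through: scoring regardless of added therapy needs scores after the event, and sections 8.4 to 8.6 generally remove them.

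**Left to the SAP.** Handling of added medication often sits in the SAP, which is not shown. Here, though, the protocol states the endpoint definition twice, in score-only terms, alongside its own reading of an upgrade as worsening. The point rests on that stated definition.

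**Medication in the model.** Section 10.2 says medication use will be considered alongside the mixed model. This reclassifies no one on a binary status, and adjusting for medication started after randomisation would condition on a post-randomisation variable.

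**Stronger readings that the documents do not support:**

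- *Every upgraded subject counts as a success.* The score criterion must also be met, and a subject stepped up for an exacerbation should have been withdrawn under 8.4.1.
- *A large share of subjects is affected.* A reader might take the entry criterion of at least one exacerbation in two years as a rate of 0.5 per year and compute 1 − exp(−0.5 × 8/52) = 7% by week 8 and 1 − exp(−0.5 × 60/52) = 44% by week 60. These are exacerbation probabilities in subjects selected for a past relapse. They do not estimate upgraded and retained subjects, and exacerbation is what 8.4.1 removes.
- *The bias must hide a benefit.* That holds only if retained upgrades are commoner in the worse arm; the reverse enlarges the difference.
- *The listed drug classes are expected upgrades.* Section 8.1.2 lists them as examples of current medication to be recorded.

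**Conclusion.** The point holds as a defect in a secondary endpoint. The wording is clear: remission and response ignore UC medication upgrades, retained upgraded subjects who meet the criterion are successes, and subjects withdrawn for an exacerbation generally become missing. Bias follows if upgrades or such withdrawals differ between arms, and it matters most at weeks 12 and 60.

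Its size and direction cannot be derived from the protocol, which gives no remission, upgrade or withdrawal-for-exacerbation rates. The tabulated shifts, from 16 points down to 16 points up, show only what assumed rates would do.

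The primary analysis of mean week-8 P-SCCAI and the 11 (15 after drop-out) per group do not depend on these definitions. This should be corrected, but it does not put the main comparison in question.

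**What to change.** In sections 8.1.2 and 10.2:

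1. Define remission and response at each visit as the P-SCCAI criterion met **and** no UC medication upgrade since T=0. For this endpoint, state what an upgrade is (a new UC agent or a dose increase, including systemic steroids).
2. From that point on, count as non-remission and non-response any subject with an upgrade, and any subject withdrawn under 8.4 or 8.4.1 for interfering medication or UC exacerbation.
3. Report the score-only version as a sensitivity analysis.
4. Reconcile the definitions in 8.1.2 and 10.2 with the medication-use paragraph of 8.1.2 and with 8.4, 8.4.1 and 8.6, so that classification does not depend on whether a subject happened to be withdrawn.

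This changes classification only, not how any subject is treated.

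**Cost.** Mainly wording. Section 10.2 already collects type, dose, frequency and duration of each medication. Two practical points follow. The week-60 extraction must cover the whole interval since week 12, not only current use. The reason for investigator-led withdrawal must be recorded; subjects may leave without giving a reason, and those remain ordinary missing data. Reported remission rates will be lower, possibly by more than a little in an arm with many upgrades: in the fourth illustrative row, the worse arm falls from 44% to 20%.

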4.4 Sample size calculation

The primary objective of the trial is to validate the prediction that a higher response (lower mean P-SCCAI score) is induced at T= 8 weeks by the prebiotics intervention in mild UC patients with low Bacteroidetes levels (predicted responders), but not in those with high Bacteroidetes levels (predicted non-responders) in their gut. Mild UC is defined as a P-SCCAI score of 3 to 5. According to an extensive study regarding UC disease activity conducted in the Netherlands, mild UC patients have a P-SCCAI score of 3.5 ± 0.5 (Mean \pm standard deviation (SD)), and patients in remission score at 1.0 ± 0.33 (Mean \pm SD)[34, 35].

In a series of germinated barley foodstuff (GBF) intervention studies, 10 mild to moderately active UC patients received 30 grams of GBF (equals to 10 grams fiber) daily for 4 weeks [4], and researchers found a significant decrease in clinical activity index scores. In a later study, another group of 11 mildly to moderately active UC patients consuming 20-30 grams of GBF (equals to 6.66-10 g fiber) daily for 4 weeks showed similar results, with decreases in clinical activity index scores [28].

Based on two-sided statistical testing for unpaired continuous data, an $\alpha=0.05$ (chance on type-I error) and $\beta=0.10$ (chance on type-II error), and assuming a 20% difference of mean P-SCCAI score between predicted responders with prebiotics and predicted non-responders with prebiotics, it was calculated that at least 11 subjects per group are needed for the primary outcome P-SCCAI ($\mu_1=3.5$; $SD_1=0.5$; $\mu_2=2.8$). According to previous trials on prebiotics on IBD patients, a 20% of drop-out rate is commonly seen. Given that the intervention duration is 8 weeks long, followed by a 1 year follow-up, higher dropout rate (30%) is expected. To compensate for a 30% drop-out rate, 15 subjects per group are needed.

To reach inclusion of 30 predicted responders and 30 predicted non-responders, we made an estimate how many subjects we need to screen based on the earlier obtained microbial composition of stool samples from UC patients in the Ede area. Around 50% of these subjects were categorized as low Bacteroidetes subjects (predicted responders) and while 17% of them as high Bacteroidetes subjects (predicted non-responders). To include these responders we will need to screen 177 mild UC patients.

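### For T=0 P-SCCAI scores of 3 to 5, clinical response is nested in clinical remission, and remission depends strongly on a T=0 score that the plan neither stratifies by nor names as a covariate

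*Protocol*

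**What the plan says.** Protocol 4.2 sets the entry range: "Mild active UC as defined by P-SCCAI score of 3 to 5 (range 0 to 19" points). Protocol 8.1.2 (Response over time) then defines two dichotomous outcomes. The first is an absolute threshold: "With P-SCCAI score <= 2 being regarded as clinical remission". The second is relative to the patient's own starting score: "a decrease in the P-SCCAI score by more than two points from baseline being regarded as clinical response". The section adds: "We will also determine whether subjects have reached clinical remission and/or showed a clinical response over time". Section 10.2 repeats both definitions and works from the summed score: "data of sum P-SCCAI score within each subject at T = 0, 4, 8, 12 and 60 weeks will be obtained".

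Section 8.3 has P-SCCAI completed in the screening package and again at baseline, after selection. No rule says that the second score must still be 3 to 5.

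Section 8.2 describes block randomisation after classification by Bacteroidetes level and names no stratification by P-SCCAI. The covariates that 10.2 gives as examples for the mixed model are BMI, age, sex and medication use.

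For size, 4.4 states that "mild UC patients have a P-SCCAI score of 3.5 ± 0.5" and plans by "assuming a 20% difference of mean P-SCCAI score between predicted responders with prebiotics and predicted non-responders with prebiotics", that is 3.5 against 2.8.

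**The concern.** A response criterion usually picks up patients who improve without reaching remission. With entry at 3 to 5 and a required drop of more than two points, this one cannot do so. A reader who sees a remission count and a response count side by side may take them as two pieces of evidence, when the second only re-counts some of the patients in the first.

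The criterion also misses improvement that the trial would want to see. A fall from 5 to 3 is 2/5 = 40%, twice the planned 20% difference, yet it meets neither definition.

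Remission has its own weakness. Its difficulty depends on where the patient starts. With 15 patients per arm, chance differences in T=0 score add avoidable noise to the comparison of remission rates.

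**Working it through.** **Plan's own figure.** Inputs from 4.4: difference 0.7, SD 0.5, two-sided alpha 0.05, power 0.90. n = 2 × (1.960 + 1.282)² × 0.5² / 0.7² = 10.7, so 11 per group, as stated. The protocol then enrols 15 per arm.

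**Nesting.** P-SCCAI is a sum of item scores; whole points are an inference. Response then means a drop of at least 3.

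| T=0 score | Final scores that count as response | Final scores that count as remission | Remission without response | Response without remission |
|---|---|---|---|---|
| 3 | 0 | 0, 1, 2 | 1, 2 | none |
| 4 | 0, 1 | 0, 1, 2 | 2 | none |
| 5 | 0, 1, 2 | 0, 1, 2 | none | none |
| 6 | 0 to 3 | 0, 1, 2 | none | 3 |

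Over T=0 scores of 3 to 5 response is a strict subset of remission; the two coincide only at 5. The row for 6 shows where the relation ends. A patient at 2 or less at T=0 is already in remission; from a score of 2, response is impossible.

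**How often response would occur.** Assumptions: the 0.7 is read as a mean drop, which is natural only because 3.5 is also the stated mean for mild UC; change is normal; its SD is 0.5 × √(2(1 − ρ)), where ρ is the correlation between baseline and week 8. The protocol gives neither ρ nor an SD of change. P(drop > 2) = 1 − Φ((2 − 0.7)/SD):

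- ρ = 0: SD 0.707, z = 1.84, 3.3% (0.5 of 15 patients)
- ρ = 0.5: SD 0.500, z = 2.60, 0.5%
- ρ = 0.7: SD 0.387, z = 3.36, 0.04%

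Simulation on whole-point scores (baseline 3.5, SD 0.5, kept within 3 to 5; week-8 mean 2.8; ρ from 0 to 0.8):

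| Week-8 SD | Response | Remission |
|---|---|---|
| 0.5 (protocol) | 0 to 0.9% | 26 to 27% |
| 1.0 (assumed) | 0.6 to 6% | 37 to 38% |
| 1.5 (assumed) | 6 to 13% | 41 to 42% |
| 2.0 (assumed) | 12 to 20% | 43 to 44% |

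**How far remission depends on the T=0 score.** Remission needs a drop of 1, 2 or 3 points from 3, 4 or 5. With whole-point rounding the cuts are 0.5, 1.5 and 2.5. P = 1 − Φ((cut − mean drop)/SD of change), with the SD assumed:

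| SD of change | From 3, drop 0.7 | From 4, drop 0.7 | From 5, drop 0.7 | From 3, no mean drop |
|---|---|---|---|---|
| 0.71 | 61% | 13% | 0.5% | 24% |
| 1.0 | 58% | 21% | 4% | 31% |
| 1.5 | 55% | 30% | 12% | 37% |

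At SD 1.0, starting at 3 rather than 4 moves remission by 58 − 21 = 37 percentage points. A mean drop of 0.7 moves it by 58 − 31 = 27 points in a patient who starts at 3.

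If half the patients start at 3 and half at 4 (which gives mean 3.5 and SD 0.5), the share of 3s differs between two arms of 15 with an SD of √(2 × 0.25/15) = 0.18. At SD 1.0 that shifts the expected difference in remission by 0.18 × 37 ≈ 7 points for a one-SD chance imbalance.

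**The case against.** **The nesting is conditional.** Eligibility rests on the screening score, while change is taken from a re-measured baseline. A patient at 6 who falls to 3 responds without remission. This stands, and the point is limited to T=0 scores of 3 to 5.

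**A reader might infer that the response endpoint adds nothing.** The documents do not support that. As a separate count, response is a stricter category: it separates 3 to 0 from 3 to 2, and 4 to 1 from 4 to 2. What adds no patients is the combination of the two.

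**A reader might infer that a formal composite is planned, or that the counts will be presented as independent evidence.** The text can equally mean that each patient is classified on both definitions. It says nothing about independence.

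**A reader might infer that response is practically unreachable.** That follows only from the planned SD of 0.5 and from treating a between-arm difference as a within-patient drop. The 0.7 is also a week-8 figure, and no effect is assumed for weeks 4, 12 or 60. With a larger SD, response is uncommon but not absent.

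**Imbalance in the T=0 score is a matter of chance, and a mean of 3.5 with SD 0.5 leaves few 5s.** Both are fair. Randomisation protects the unadjusted comparison from systematic bias, so the gain from adjustment is precision and protection against a chance imbalance. The working therefore also sets 3 against 4, and the dependence remains large.

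**Some of this is already covered, or is a matter for the SAP.** The mixed model in 10.2 includes T=0 among its time points, so mean change is partly covered. Its covariate list is open, and further detail may sit in an analysis plan. The thresholds, however, are fixed in the protocol. They may come from the published sources it cites, and keeping them for comparison with other studies is defensible.

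**Conclusion.** The point holds in a limited form. For whole-point T=0 scores of 3 to 5, response is nested in remission, so counting patients with either outcome gives the remission count. Response is also the harder of the two to reach. This is exact and rests on no distributional assumption.

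The expected frequency is less certain: about 0 to 3% of an arm at the protocol's SD of 0.5, about 6 to 13% at an SD of 1.5 and 12 to 20% at 2.0. The two larger SDs, the correlation and the reading of 0.7 as a mean drop are assumptions.

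The practical consequence lies with remission. Its probability falls steeply as the T=0 score rises, and that score is neither a stated stratification factor nor a named covariate. This concerns a secondary outcome. The comparison of mean P-SCCAI at week 8 and its sample size are untouched, so the matter is minor.

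**What to change.** In 8.1.2 and 10.2:

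1. Use change in P-SCCAI, adjusted for the T=0 P-SCCAI, as the measure of improvement.
2. Compare remission between arms with adjustment for the T=0 P-SCCAI.
3. If the response count is kept for comparison with other studies, report it separately. State that for T=0 scores of 3 to 5 it is nested in remission and is not independent evidence.

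The T=0 score is already collected, so no new data or patients are needed. The cost is some rewording and a little more analysis. With about 11 to 15 patients per arm, the adjusted remission model may need a small-sample method. Rewording the and/or sentence alone would change no result; the adjustment is the useful part.

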At the end of the intervention period (T= 8 weeks), the participants will be asked to return everything (used and unused sachets) to the coordinating investigator to determine compliance to the study.

Follow-up period (4 weeks and 52 weeks)

During the follow-up period, participants will not take supplements anymore.

At T=12, and 60 weeks, P-SCCAI (once a week) and medication use (once a week) will be completed.

At T=12, and 60 weeks, one time stool sample will be collected at each time point. These samples will be used for fecal calprotectin measurements, 16S rRNA gene-based microbiota profiling, and SCFAs profile analysis.

We will determine response with P-SCCAI score at T= 12, and 60 weeks.

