8.4 Withdrawal of individual subjects

Subjects can leave the study at any time for any reason if they wish to do so without providing a reason and without any consequences. The investigator can decide (upon consultation with the medical supervisor) to withdraw a subject from the study for urgent medical reasons, such as serious GI complaints, negative reactions upon supplement intake, etc., or when study participants have to start medication that interferes with outcomes during the study period.

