8.4.1 Specific criteria for withdrawal

A subject will be withdrawn from the study in the case of serious gastro-intestinal complaints or an exacerbation of UC reported by the subjects (such as continuous diarrhea or constipation, bloating, abdominal pain).

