8.6 Follow-up of subjects withdrawn from treatment

After possible withdrawal, no follow-up of research subjects will take place, except in case of withdrawal for other medical reasons.

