9.4 Follow-up of adverse events

All AEs will be followed until they have abated, or until a stable situation has been reached. Depending on the event, follow up may require additional tests or medical procedures as indicated, and/or referral to the general physician or a medical specialist. SAEs need to be reported till the end of study within the Netherlands, as defined in the protocol.

9.5 [Data Safety Monitoring Board (DSMB) / Safety Committee]

Not applicable.

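### The withdrawal rules in 8.4.1 and 8.6 do not secure medication extraction after a reported flare, so later upgrades can be missed for secondary objective 7

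*Protocol*

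**What the plan says.** Secondary objective 7 (Protocol section 2) concerns the effect of the prebiotics on medication use. Section 8.1.2 takes this from patient record and diary at baseline and weeks 4, 8, 12 and 60. It states that the later changes "provide information on disease development, with a downgrade means improvement and an upgrade means worsening of UC". Section 8.3 repeats the late time points: "At T=12, and 60 weeks, P-SCCAI (once a week) and medication use (once a week) will be completed".

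Three rules decide who is still observed:

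- 8.4.1, mandatory: "A subject will be withdrawn from the study in the case of serious gastro-intestinal complaints or an exacerbation of UC reported by the subjects".
- 8.4, at the investigator's discretion after consulting the medical supervisor: withdrawal for urgent medical reasons, "or when study participants have to start medication that interferes with outcomes during the study period".
- 8.6: "After possible withdrawal, no follow-up of research subjects will take place, except in case of withdrawal for other medical reasons".

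Two other passages bear on what is captured. Section 9.4 says "All AEs will be followed until they have abated, or until a stable situation has been reached" and has SAEs reported to the end of the study. The safety paragraph of 8.1.2 says "At T= 0, 4, and 8 weeks, safety parameters (i.e., incidence of adverse events) will be monitored by patient record and diary", and its diary records steroid need, hospital admission and surgery linked to relapse.

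**The concern.** The event that the endpoint counts as worsening is closely tied to the event that can end its observation. A patient who flares is the one most likely to step up UC medication, and a reported flare requires withdrawal. If extraction then stops, the missing data depend on the outcome itself. They cannot be treated as ordinary drop-out.

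The matter is relevant to this population, because 4.2 requires a relapse within the two years before entry and observation runs to week 60. It also has to be settled in the protocol. An analysis plan can choose how to handle missing medication data, but it cannot recover data that nobody extracted or that consent did not cover.

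**Working it through.** The protocol states no figure for medication upgrades or flare withdrawals, so there is nothing to reproduce. The check sets the sections side by side and then asks what can be bounded.

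**Step 1: two readings of the exception in 8.6.**

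- Reading A: it contrasts medical with personal reasons. A flare is a medical reason, so follow-up continues. Section 8.6 does not say what that follow-up contains, and no other section assigns scheduled medication extraction to withdrawn patients.
- Reading B: it means reasons other than those already named in 8.4 and 8.4.1. A flare is then outside the exception and follow-up ends.

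**Step 2: extractions at risk.** There are four after baseline: weeks 4, 8, 12 and 60. For a flare reported at a scheduled contact, with that contact's extraction completed:

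| Flare reported | Extractions remaining | Secured under A | Under B |
|---|---|---|---|
| Week 4 | 8, 12, 60 (3 of 4) | not stated | stop |
| Week 8 | 12, 60 (2 of 4) | not stated | stop |
| Week 12 | 60 (1 of 4) | not stated | stop |

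No assessment is scheduled in the 60 − 12 = 48 weeks between the last two time points. A flare in that interval that the patient does not report need not lead to withdrawal, and its treatment can still be found in the record at week 60. The gap therefore mainly concerns flares reported up to week 12.

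**Step 3: what other sections catch.** An upgrade made at or before withdrawal may already be in the record or diary. Treatment of the flare itself can be caught through 9.4 while the event is open. A further step-up after the flare has settled falls outside 9.4 unless it belongs to a new SAE. The safety diary has scheduled time points at weeks 0, 4 and 8 only. None of these provides medication extraction at weeks 12 and 60 after withdrawal.

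**Step 4: bounds.** In one treatment group, let W be the patients withdrawn for a flare who escalate by week 60, and r those among them with an upgrade already on file. The number of patients whose upgrade is missed is M = W − r, with 0 ≤ M ≤ W. If r = W, then M = 0, although later changes in the same patients are still lost. The error in the between-treatment comparison depends on M in each group and can go either way. The documents give neither W nor r.

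The nearest figure is in 4.4: "followed by a 1 year follow-up, higher dropout rate (30%) is expected". Applied to 60 patients this is 0.30 × 60 = 18, but it covers all causes and the whole study, and no flare share is given. It cannot stand in for W.

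**The case against.** The strongest reply is that Reading A is the natural one. Section 8.4 first describes leaving at the patient's own wish and then withdrawal on urgent medical grounds, and 11.6 draws a similar line for payment. Reading B would follow patients withdrawn for unrelated illness and drop those withdrawn for the disease under study. It also sits badly with 9.4, since a flare is an adverse event under 9.2.1. This carries weight: Reading A may well be what was meant. It does not close the gap, because 8.6 does not say under Reading A that medication is still extracted.

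A second reply is that handling withdrawals belongs in the analysis plan. This stands in part. Whether a flare withdrawal counts as an upgrade is an analysis definition, and the reason for such a withdrawal is known, so an analysis plan could code it as worsening. The mixed model in 10.2 can use the visits before withdrawal. Neither supplies the type, dose, frequency and duration of medication at time points that were never extracted.

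Three stronger readings are tempting, and the documents do not support them:

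- A reader might infer that the protocol certainly drops patients who flare. The exception in 8.6 leaves that open, and withdrawal for starting medication under 8.4 is discretionary.
- A reader might infer a definite shrinkage of the treatment difference by treating the 30% drop-out as escalators lost without record. That figure covers all causes over the full study, while the gap lies mainly before week 12. The first escalation may also be captured, and no section says that lost patients leave the denominator.
- A reader might extend the point to the primary comparison at week 8. Nothing shown here bears on it.

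**Conclusion.** The point holds in limited form. After withdrawal for a reported flare, the protocol does not secure the medication extraction that 8.1.2 schedules to week 60: on one reading of 8.6 it stops, and on the other its continuation is not stated. Upgrades after withdrawal can be missed for secondary objective 7.

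Size and direction cannot be computed from the documents. The number of patients whose upgrade is missed runs from none, if the first escalation is always on file at or before withdrawal, to all flare-withdrawn patients who escalate. The conclusion rests on the wording of 8.4.1, 8.6, 8.1.2 and 9.4, and on no assumed rate. This is a low-cost improvement to one secondary endpoint.

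**What to change.** Add to 8.6: *Withdrawal for a UC exacerbation, or for starting UC medication, falls within this exception. With consent, UC medication continues to be extracted from the patient record at the remaining scheduled time points up to week 60.*

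The withdrawal rules in 8.4 and 8.4.1 stay as they are. A sentence in 8.1.2 on whether an escalation that leads to withdrawal counts as an upgrade is optional and can be left to the analysis plan.

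The cost is two sentences, consent wording for reading the record after withdrawal, and some additional record extraction. No visit or stool sample is added, and the patient record is already a stated source.
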